4. TRIAL DESIGN

This study consists of two substudies (inpatient and outpatient studies), each of which is a nonrandomised intervention study with before and after comparison. The outpatient study also includes an embedded qualitative substudy for a subset of consultations, with patient and clinician interviews. A subset of clinicians will also be interviewed for the inpatient study. The overall clinician participant flow is illustrated in Figure 2.

[figure not shown]

Figure 2: Study flow diagram showing how clinicians will move through the study

Three time periods will be analysed. The primary comparison will be for recording of structured information in patient records between pre-MiADE and post-MiADE periods once clinicians have been consented into the study, as they will have received training and the comparison will show the change in behaviour that results from the system being available. There is a possibility that structured recording may improve because of the study itself (i.e. a Hawthorne effect), so a prior 8week period will also be studied in order to evaluate this effect. See figure below for the overall trial design and timing of interventions. The overall study timeline is shown in Figure 3.

The MiADE system will be made available according to clinician-level permissions, which can be switched on or off. This will allow clinicians' use of problem lists and other structured data to be compared before and after the system is switched on. There will be a period of at least 4 weeks between clinicians entering the study and having the MiADE system switched on.

[figure not shown]

Figure 3: Study timeline

Training programme

All clinicians in the study will undergo a standardised training package consisting of viewing a video and reading a user guide, with access to help from the research team by email or phone throughout the study. The training will cover:

- The importance of maintaining problem lists with accurately coded information about a patient's diagnoses
- National and local (UCLH) guidance on the use of problem lists
- How to use the MiADE system
- The aims and methods of the study

Clinicians will not be eligible to enter the study and have the MiADE system switched on for their EHR user profile until they have undertaken the training.

Pre-MiADE questionnaire – questions for all clinicians

- What is your seniority (e.g. FY1, Consultant etc.)?
- What is your specialty?

Pre-MiADE questionnaire – outpatient study

- Regarding the recording of problems or diagnoses:
 - How frequently do you enter problem list entries or diagnoses when seeing a patient in clinic? [Never Rarely Sometimes Usually Always]
 - How easy or difficult did you find it to use the Epic interface for entering problems or diagnoses? [Very difficult – Difficult – Neither easy nor difficult – Easy – Very easy]
 - How important do you feel it is to have structured information about problems in the health record? [Very unimportant – Unimportant – Neither important nor unimportant – Important – Very Important]
- Regarding the recording of medications:
 - How frequently do you enter medications in the structured medications section when seeing a patient in clinic? [Never – Rarely – Sometimes – Usually – Always]
 - How easy or difficult do you find it to use the Epic interface for entering medications in the structured medications section? [Very difficult – Difficult – Neither easy nor difficult – Easy – Very easy]
 - How important do you feel it is to have structured information about medications in the health record? [Very unimportant – Unimportant – Neither important nor unimportant – Important – Very Important]
- Regarding the recording of allergies or medication intolerances:
 - How frequently do you enter allergies or medication intolerances seeing a patient in clinic? [Never – Rarely – Sometimes – Usually – Always]
 - How easy or difficult did you find it to use the Epic interface for entering allergies and medication intolerances? [Very difficult – Difficult – Neither easy nor difficult – Easy – Very easy]

 How important do you feel it is to have structured information about allergies in the health record? [Very unimportant – Unimportant – Neither important nor unimportant – Important – Very Important]

Pre-MiADE questionnaire – inpatient study

- Regarding the recording of problems or diagnoses:
 - How frequently do you enter problem list entries or diagnoses when clerking a patient or reviewing a patient on a ward round? [Never – Rarely – Sometimes – Usually – Always]
 - How frequently do you enter problem list entries or diagnoses when completing a discharge summary? [Never – Rarely – Sometimes – Usually – Always]
 - How easy or difficult did you find it to use the Epic interface for entering problems or diagnoses? [Very difficult – Difficult – Neither easy nor difficult – Easy – Very easy]
 - How important do you feel it is to have structured information about problems in the health record? [Very unimportant – Unimportant – Neither important nor unimportant – Important – Very Important]
- Regarding the recording of allergies or medication intolerances:
 - How frequently do you enter allergies or medication intolerances when clerking a patient or reviewing a patient on a ward round? [Never – Rarely – Sometimes – Usually – Always]
 - How frequently do you enter allergies or medication intolerances when completing a discharge summary? [Never Rarely Sometimes Usually Always]
 - How easy or difficult did you find it to use the Epic interface for entering allergies and medication intolerances? [Very difficult – Difficult – Neither easy nor difficult – Easy – Very easy]
 - How important do you feel it is to have structured information about allergies in the health record? [Very unimportant – Unimportant – Neither important nor unimportant – Important – Very Important]

Post-MiADE questionnaire

After MiADE has been switched on and clinicians have been using it for at least two weeks, they will be asked to fill in a survey questionnaire with the following questions:

- How many weeks have you been using the MiADE system?
- Regarding the recording of problems or diagnoses:
 - How frequently did you use MiADE for entering problem list entries or diagnoses? [Never – Rarely – Sometimes – Usually – Always]
 - When using MiADE for entering problems or diagnoses, were the suggested SNOMED CT concepts correct? [Never Rarely Sometimes Usually Always]

- How easy or difficult did you find it to use the MiADE system for entering problems or diagnoses? [Very difficult – Difficult – Neither easy nor difficult – Easy – Very easy]
- How useful did you find the MiADE system for entering problems or diagnoses? [Not at all useful Somewhat useful Useful Very useful]
- Regarding the recording of allergies and medication intolerances:
 - How frequently did you use MiADE for entering allergies and medication intolerances? [Never Rarely Sometimes Usually Always]
 - When using MiADE for entering allergies and medication intolerances, were the suggested entries correct? [Never Rarely Sometimes Usually Always]
 - How easy or difficult did you find it to use the MiADE system for entering allergies and medication intolerances? [Very difficult – Difficult – Neither easy nor difficult – Easy – Very easy]
 - How useful did you find the MiADE system for entering allergies? [Not at all useful Somewhat useful – Useful – Very useful]
- How do you think MiADE could be improved? [free text]
- How do you think the Epic user interface for entering structured information could be improved? [free text]

Post-MiADE questionnaire – additional questions for clinicians in outpatient study

- How many clinics have you conducted with the MiADE system? (*only for clinicians in outpatient study*) [free text]
- Regarding the recording of medications:
 - How frequently did you use MiADE for entering medications during an outpatient consultation? [Never Rarely Sometimes Usually Always]
 - When using MiADE for entering problems or diagnoses, were the suggested medications and dosages correct? [Never Rarely Sometimes Usually Always]
 - How easy or difficult did you find it to use the MiADE system for entering medications? [Very difficult Difficult Neither easy nor difficult Easy Very easy]
 - How useful did you find the MiADE system for entering medications? [Not at all useful – Somewhat useful – Useful – Very useful]

Post-MiADE interview prompts

- In your experience, how completely are problems, medications and allergies recorded in clinical practice?
- Why do you think this is?
- How effective do you feel MiADE is in increasing the recording of structured information about problems, medications, allergies and medication intolerances?
- Why do you think this is?
- How do you think MiADE could be improved?

- How do you think the Epic user interface for entering structured information could be improved?
- What else needs to change to improve the recording of structured information?

Study 1 (Outpatient study)

Consultants and specialty doctors who see outpatients will be recruited via institutional communications and networks. Interested clinicians will be consented and receive training on the use of the system, as described below. They will be asked to fill in a survey on their level of experience and comfort with EHR systems. They will have the MiADE system switched on within their EHR user profile so that they have access to it from a particular date. Electronic health records of outpatients in the clinics linked to the clinician will be assessed for 3 time periods: pre-study (before the training session), between the training session and MiADE switch-on, and for 8 weeks after MiADE is switched on. The crude number of entries per patient in the problem list, medication record and allergy record will be calculated for outpatients seen by the clinician during each interval.

Embedded qualitative substudy

For each clinician in the qualitative substudy, a sample of at least 2 outpatient consultations will be observed before the MiADE system is switched on for the clinician, and at least 2 outpatient consultations will be observed after the MiADE system is switched on. For each observed consultation, consent will be sought from the patient prior to the consultation. The researcher will sit in the consultation and observe the overall consultation, as well as timing the overall consultation and how long the clinician spends interacting with the EHR. The researcher will ask questions to the clinician after the consultation, if necessary, in order to clarify any behaviours observed.

Patient interviews

A semi-structured interview will be held with the patient after the consultation either in person (if clinic space is available) or by telephone, to explore the patient's perception and experience of the consultation.

The interview guide will include questions such as:

- How did you feel about the way that the doctor interacted with the computer in your consultation?
- How did this compare with your experience of previous consultations in this hospital or elsewhere?
- Use and usefulness of the UCLH patient portal (MyCare): prompts include
 - Access to medical diagnoses, allergies and medications on the UCLH patient portal
 - Usefulness of the features
 - Completeness and accuracy of the information
- Would you be interested in being invited to future workshops or other activities to help improve electronic health records?

Study 2 (Inpatient study)

Inpatient clinical teams will be recruited to the study. Within each team, the clinicians (consultants, specialty and foundation doctors who see inpatients) will be recruited, consented and trained. Doctors rotate through clinical teams every few months, so the MiADE system will be switched on for the relevant clinicians at a time point half-way through the four-month rotation, to allow comparison of the completeness of structured recording of diagnoses on the problem list before and after the switch-on. The 'gold standard' of recording of diagnoses will be the ICD-10 coded billing diagnoses which are assigned by the clinical coding team based on a review of the entire medical record after a patient is discharged. Diagnoses will be aggregated by groups of ICD-10 codes similar to a previous UCLH audit [15], and a diagnosis will be considered as included in the problem list if any SNOMED CT concept which maps to an ICD-10 code in the group was recorded on or prior to the patient's discharge date. This flexibility of mapping will be permitted as different professionals may assign different clinical codes to the same condition based on their interpretation and judgement, especially for cases where an exact code does not exist. The proportion of ICD-10 code groups with a problem list entry will be calculated per patient, and aggregated across the patients under the care of the clinical team during the study period.

For a sample of 5 clinicians, semi-structured interviews will be held with the clinicians after they have been using MiADE for at least two weeks, using the same questions as for outpatient doctors except the question on medications, as MiADE for inpatients does not handle medications.

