10.6.3 Secondary outcome analysis

The electronic health record system audit logs will be used to assess whether each structured data item suggested by MiADE is accepted by the clinician. Descriptive statistics will be calculated for this proportion among subgroups such as inpatients and outpatients, and the distribution among clinicians in the study will be calculated.

The distribution of computing times per consultation note will be calculated and summarised (mean, standard deviation, median and interquartile range).

Descriptive statistics will be calculated for each of the survey questions.

A full descriptive analysis of qualitative data will be conducted to meet study objectives. Interview transcripts and observation notes will be analysed using thematic coding mapped to the theoretical domains framework to understand the cognitive, affective, social, environmental, organisational and professional influences on behaviours relating to the use of MiADE. A researcher will code emerging themes drawing on the theoretical frameworks that underpin the interview schedule and topic

guide. An iterative approach using constant comparison will be employed in the development of coding frames and coding of data. A second researcher will read all the transcripts and code a sample to ensure reliability. Emerging themes from patient interviews will be discussed at team meetings and shared with our patient representatives to confirm that interpretations made by researchers stay close to the direct experience of patients

Interview findings from patient and clinician interviews will be transcribed, coded and findings aggregated into themes.

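### Post-MiADE questionnaire: the accuracy, ease and usefulness items have no non-use option, so *Never* on accuracy can mean either never correct or not used

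*Protocol*

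**What the plan says.** Section 4 of the protocol (Post-MiADE questionnaire) gives the items and their response options in full. For problems and allergies, and in the outpatient supplement for medications, the order is the same: frequency of use, correctness of suggestions, ease, usefulness.

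- Use, allergies: "How frequently did you use MiADE for entering allergies and medication intolerances? [Never Rarely Sometimes Usually Always".
- Accuracy, allergies: "When using MiADE for entering allergies and medication intolerances, were the suggested entries correct? [Never Rarely Sometimes Usually Always". Problems have the parallel item: "When using MiADE for entering problems or diagnoses, were the suggested SNOMED CT concepts correct? [Never Rarely Sometimes Usually Always".
- Ease: "How easy or difficult did you find it to use the MiADE system for entering problems or diagnoses", on a five-point scale from very difficult to very easy with a neutral midpoint.
- Usefulness: "How useful did you find the MiADE system for entering problems or diagnoses? [Not at all useful Somewhat useful Useful Very useful".

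None of the accuracy, ease or usefulness items prints an option for a clinician who did not use MiADE in that domain, and no routing rule is written.

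Section 4 times the survey "After MiADE has been switched on and clinicians have been using it for at least two weeks". Section 7.3.2 asks only that clinicians have had access for at least 2 weeks. Section 6.1 says a clinician may decline to use MiADE or ignore its output, and the risk table in section 11 adds that it can be switched off at any time. For the analysis, section 10.6.3 states: "Descriptive statistics will be calculated for each of the survey questions". It does not condition any item on use.

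**The concern.** The use item and the accuracy item share one Never-to-Always scale. A clinician who never used MiADE for allergies, and says so, meets the accuracy item next. The choices are to leave it blank or pick a substantive answer, and *Never* is an easy one to pick. On the data sheet that response looks the same as a report that the suggestions were never right. Non-use in a single domain is foreseeable: someone may use MiADE for problems and not for allergies, and the *Never* option on each use item shows that the protocol allows for it.

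Usability is the first secondary objective (section 3.2), clinician perception is a listed secondary outcome (section 3.3), and section 20 says the anonymised survey findings will be made public. If uptake in a domain is low, an unconditioned summary of the accuracy item would mix low uptake with poor performance. Those two results call for different improvements to the system.

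**Working it through.** The plan states no figure on this point, so there is none to reproduce. The check is a reading of the printed options followed by share arithmetic.

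**Step 1: response options.** Accuracy has five options, ease five and usefulness four. None of them covers non-use. The use item has five, one of which is *Never*.

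**Step 2: can a non-user be a respondent?** Section 4 describes respondents as having used the system for two weeks. Section 7.3.2 requires access only, and sections 6.1 and 11 permit non-use. Even on the stricter reading in section 4, use of the system as a whole does not imply use in every domain. So yes.

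**Step 3: possible size.** Let *N* be respondents, *m* the number who did not use MiADE in the domain, and *p* the share of users answering *Usually* or *Always*. If all *m* tick *Never* on accuracy, the reported share is (N − m) × p / N.

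Inputs: N = 25 (minimum clinicians per substudy, section 10.4) and N = 50 (target), assuming everyone responds. The protocol gives neither p nor m. I assume p = 80% and show a range for m.

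| N | m | Reported *Usually*/*Always* | *Never* share, if no user ticks it |
|---|---|---|---|
| 25 | 0 | 25 × 0.8 / 25 = 80% | 0% |
| 25 | 2 | 23 × 0.8 / 25 = 73.6% | 8% |
| 25 | 5 | 20 × 0.8 / 25 = 64% | 20% |
| 25 | 10 | 15 × 0.8 / 25 = 48% | 40% |
| 50 | 5 | 45 × 0.8 / 50 = 72% | 10% |
| 50 | 10 | 40 × 0.8 / 50 = 64% | 20% |
| 50 | 20 | 30 × 0.8 / 50 = 48% | 40% |

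If non-users leave the item blank, the share stays at 80%. With 5 non-users among 25, the bias therefore lies between 0 and 16 percentage points (80 − 64), depending on how many of them answer.

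**Step 4: does filtering on the use item repair it?** Only in part. The use item asks about using MiADE for entering data. Section 6.1 says suggestions are displayed beside the draft note and the clinician clicks to add each one. A clinician who saw allergy suggestions, judged them all wrong and added none could truthfully answer *Never* to both items.

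Take N = 25, with 5 answering *Never* to use and all 5 ticking *Never* on accuracy. Suppose *k* of the 5 saw suggestions and rejected them as wrong. The share among those with a real basis for rating is 20 × 0.8 / (20 + k) = 16 / (20 + k). This runs from 80% (k = 0) to 64% (k = 5). The unfiltered summary reports 64% and the filtered one 80%, whatever k is. Each is right only at one end, and the survey as printed does not record k.

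**The case against.** The strongest reply is that the survey already identifies non-users. In each domain the use item comes immediately before the accuracy item and accepts *Never*, so an analyst can condition on it. Denominators for a descriptive summary are commonly settled in a statistical analysis plan, which is not shown. The accuracy items open by referring to use of MiADE, section 9.2 says the survey is electronic, and the tool may have routing that the protocol does not describe. Acceptance of suggestions is measured separately from audit logs (section 10.6.3), and interviews and free-text questions also cover perceptions.

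Much of this stands. A reader might infer that non-users have no valid answer anywhere in the survey. That is not so, because the use item gives them one. A reader might also infer that the ratings are distorted as a matter of fact. The documents support only that the accuracy rating can be, if non-users answer and are not separated out. No direction can be claimed for ease: that item has no *Never* option, and a non-user could leave it blank or choose the midpoint.

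It is also tempting to read the usefulness options ("Not at all useful Somewhat useful Useful Very useful") as a biased scale, with one unfavourable option, three favourable and no neutral. The documents do not support that. It is a unipolar scale running up from zero, which needs no neutral midpoint. Reported category by category it does not mislead, and the protocol nowhere plans to pool the upper three.

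What the reply does not answer is Step 4. Filtering on use cannot separate a clinician who saw only wrong suggestions from one who saw none, and audit logs record acceptance, not perceived correctness. The response options are fixed in the protocol text, so this is not a detail left to an analysis plan.

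**Conclusion.** The concern holds in a limited form. The accuracy, ease and usefulness items lack a non-use option and a stated skip rule, and *Never* on accuracy has two meanings that the printed survey cannot fully separate. The accuracy rating can be biased downward. With no non-users the bias is zero. With 20% non-users who all tick *Never*, and 80% of users answering favourably, it is 16 percentage points (80% to 64%). The 80%, the non-user share and the assumption that every non-user ticks *Never* and saw no suggestions are illustrations, not figures from the protocol, so the actual size is unknown. The stakes are modest: these are descriptive secondary items in a feasibility study, and neither primary outcome is touched. The change is still worth making before the post-MiADE round, because the ambiguity cannot be fully undone once answers are in.

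**What to change.** In the post-MiADE questionnaire, add one response option to each accuracy, ease and usefulness item for problems, allergies and medications, worded along the lines of *Did not use MiADE for this / saw no suggestions*. Put it on the item itself rather than routing people past it from the use item, so that clinicians who saw suggestions and rejected them can still rate them. In section 10.6.3, state that each of these items is summarised among those giving a substantive answer, with the number choosing the new option shown beside it. Keep the four-point usefulness scale and report it category by category.

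The cost is an edit to the electronic survey and a minor amendment. The downside is smaller denominators for these items, which matters somewhat with as few as 25 clinicians per substudy.

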7.3 Baseline and Intervention Procedures

7.3.1 Baseline data

Clinician participants: A baseline questionnaire will be administered to gather information about specialty, seniority, and self-rated level of expertise with the electronic health record system.

Patient participants: All data on patients will be collected as part of the interview after the observed consultation. This will include questions on patient characteristics including age group, gender and ethnicity. This information will be collected to ensure the diversity of the patient sample.

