7.3.2 Intervention Procedures

Clinician participants: Clinicians will be consented and asked to watch a training video on the need for structured data recording and how to use the MiADE system. They will then be asked to fill in a pre-MiADE questionnaire survey on their experience of using the electronic health record system.

Clinicians in the qualitative substudy will be observed for at least 4 face to face consultations (2 before MiADE and 2 after) for which patients have given consent. They will also be interviewed after using MiADE. The time period between consent and having the MiADE system switched on will be at least 4 weeks. Patient participants in the qualitative substudy will be consented prior to their consultation and the researcher will sit in the consultation to observe the interactions between doctor, patient and the computer. A purposive sample of 5 clinicians (covering a range of inpatient teams and levels of seniority) from the inpatient substudy will also be interviewed post MiADE switch on, around the time of the questionnaire survey.

During the observed consultations, the researcher will make notes but no recording devices will be used. The researcher will leave the room or stay outside the curtains if the patient is being examined. After the consultation, the researcher may ask questions of the clinician in order to clarify any behaviours or events that were observed.

Patients will be invited to participate in an interview following the consultation. This may be immediately after the consultation or by telephone or virtually at a convenient time for them. Interviews will explore individuals' experience, understanding and perception of the MiADE system. The interview questions will be informed technology evaluation and behavioural change theories and developed from relevant literature and the experience of the research team. The interview schedule will mainly comprise open questions to allow patients to provide their own perspectives,

be iterated in consultation with our patient and public partners and piloted before use to ensure face validity.

We anticipate a total of 10-15 interviews for patients for each phase, although this will be subject to saturation checking. Through targeted patient recruitment we will ensure, as far as possible, that the interview sample reflects diversity with respect to gender, age, ethnicity and any other characteristics identified as important during the data collection period.

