10.6.4 Sensitivity and other planned analyses

Subgroup analyses for the completeness of structured data recording will be carried out by clinical specialty and seniority of doctor. Correlations between clinician characteristics in the pre-MiADE survey and the difference in mean number of structured entries with MiADE for outpatients will be explored.

Secondary analyses will be carried out to compare recording of structured data between the following time periods:

- 1. Before consent versus before MiADE. This will assess the Hawthorne effect, i.e. if there is any change in clinician behaviour once they know they are in the study. This will provide useful information for future interventions to improve structured data recording.
- 2. Before consent versus after MiADE. This will assess the overall effect of the complex intervention (i.e. the whole programme of training, institutional buy-in for quality improvement, as well as the tool to assist clinicians).

There are no relevant stopping criteria.

11.ASSESSMENT AND MANAGEMENT OF RISK

The table below summarises the risks and mitigations of all interventions above standard care that are being performed:

Intervention	Potential risk	Risk Management
Entering clinical data using MiADE	MiADE may return an inaccurate suggestion (possible)	The clinician has to actively review a suggestion in order to add it to the record, so there is minimal risk that an incorrect entry will be added to the patient record.
Entering clinical data using MiADE	Clinicians may not use the system appropriately (possible)	Training will be provided and access will be limited to clinicians who have completed training.
Entering clinical data	The MiADE system may malfunction	The MiADE system is separate from Epic and works in the

using MiADE	(unlikely)	background, so users can continue with their Epic work regardless of the activity of MiADE. If Epic does not receive a reply from MiADE in a reasonable time it will timeout the request. If the MiADE system is completely down, clinicians will be able to use Epic just as before, without MiADE.
Entering clinical data using MiADE	The MiADE system may perform poorly and be a hindrance to clinicians (unlikely)	Clinicians can choose to ignore the recommendations from MiADE or switch the system off at any time.

12.RECORDING AND REPORTING OF ADVERSE EVENTS

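### The printed clinician questionnaire has no EHR-expertise item, although the protocol says one is collected, and its medication-accuracy question carries the stem for problems and diagnoses

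*Protocol*

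**What the plan says.** Section 7.3.1 states: "A baseline questionnaire will be administered to gather information about specialty, seniority, and self-rated level of expertise with the electronic health record system". The Study 1 description in Section 4 says of outpatient clinicians: "They will be asked to fill in a survey on their level of experience and comfort with EHR systems".

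Section 4 also prints the questionnaires. The pre-MiADE form asks every clinician for seniority and specialty. It then asks, by data type, how often structured entries are made, how easy the Epic interface is for making them, and how important structured information is.

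The post-MiADE form asks, by data type, about frequency of use, correctness of suggestions, ease and usefulness. Outpatient clinicians get an extra block on medications, and its correctness item reads "When using MiADE for entering problems or diagnoses, were the suggested medications and dosages correct".

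Two analyses use the survey answers. Section 10.6.3 promises descriptive statistics for every question. Section 10.6.4 will explore "Correlations between clinician characteristics in the pre-MiADE survey and the difference in mean number of structured entries" for outpatients.

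**The concern.** These are faults in an instrument that clinicians will answer as printed. If it is issued verbatim, a characteristic that the protocol says it collects will not exist in the data. Analysis cannot recover it, and an expertise rating requested later would follow exposure to MiADE and no longer be a clean pre-exposure characteristic.

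The medication item bears on a stated secondary objective, the accuracy of MiADE (Section 3.2). A respondent could answer for all medication suggestions, only for those shown while entering problems, or for the problem suggestions themselves. The descriptive summary of that item would mix these readings with no means of separating them.

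**Working it through.** The protocol gives no figure to reproduce, so the check sets the descriptions beside the printed items.

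**1. Expertise: described content against printed content**

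| Characteristic promised | Where promised | Printed item in Section 4 |
|---|---|---|
| Specialty | 7.3.1 | Yes |
| Seniority | 7.3.1 | Yes |
| Self-rated EHR expertise | 7.3.1 | None |
| Experience and comfort with EHR systems | Section 4, Study 1 | No direct item; Epic ease items are a partial proxy for comfort |

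The outpatient pre-MiADE form has 2 general items plus 3 items (frequency, ease, importance) for each of 3 data types: 2 + 3 × 3 = 11. The inpatient form has 2 general items plus 4 items (two on frequency, one each on ease and importance) for each of 2 data types: 2 + 4 × 2 = 10. None of the 11 or the 10 asks clinicians to rate their own EHR expertise or state their experience. The ease items rate the interface for one task, which is a different quantity.

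A separate baseline form could explain the gap, but the schedule in Appendix 1 contains only one survey before switch-on, the pre-MiADE survey. The questionnaire of Section 7.3.1 is therefore the one printed in Section 4, and 2 of its 3 declared characteristics are asked.

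**2. Medication accuracy: three parallel items**

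| Block | Data type named in the stem | Suggestions being rated |
|---|---|---|
| Problems | Problems or diagnoses | SNOMED CT concepts |
| Allergies and intolerances | Allergies and intolerances | Suggested entries |
| Medications (outpatient) | Problems or diagnoses | Medications and dosages |

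Two of the three correctness items name their own data type. The medication item repeats the stem of the problems item, which looks like a copying slip. The other three items in the medication block name medications correctly.

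No other survey item covers this ground. Section 4 (Study 2) says the inpatient version of MiADE does not handle medications, so only the outpatient form rates them. The audit logs in Section 10.6.3 record whether a suggestion was accepted. Section 6.1 lets clinicians ignore results, so a correct suggestion may go unaccepted, and acceptance does not stand in for rated correctness.

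**3. What depends on the survey**

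- Primary outcomes (10.1, 10.6.2): taken from health records; not affected.
- Acceptance proportion (10.6.3): taken from audit logs; not affected.
- Subgroups (10.6.4): specialty and seniority, both asked; not affected.
- Item-by-item descriptive statistics (10.6.3): one item ambiguous.
- Exploratory outpatient correlations (10.6.4): possible for every printed item, but not for expertise.

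**The case against.** The strongest reply is that both points are editorial. No planned analysis names EHR expertise, and Section 10.6.4 refers only to clinician characteristics in general. The frequency and ease items partly cover experience and comfort, and aligning the descriptions with the printed form would remove the contradiction equally well. The medication item sits inside the medication block and its object is medications and dosages, so most respondents would probably infer the intent.

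Much of this stands, and it limits the severity. It does not remove the points. The protocol lists expertise as collected and no question collects it. A question whose meaning has to be inferred is a poor basis for the only survey rating of its kind.

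A reader might infer two stronger claims:

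- **That the survey cannot support the analyses.** The documents do not bear this out. Section 3 of the working shows that only one correlate and one descriptive item are affected.
- **That the survey is wrongly timed because it follows training.** Training does cover the importance of coded problem lists, and the survey then asks about importance and frequency. But the order is stated consistently. Section 7.3.2 says, after the training video, "They will then be asked to fill in a pre-MiADE questionnaire survey on their experience of using the electronic health record system". Study 1 in Section 4 gives the same sequence, and Appendix 1 puts training at visit 1 and the survey at visit 2. Section 4 also deliberately takes the trained, pre-switch-on period as the reference for the primary comparison, so measuring clinicians in that state is defensible. No change in survey answers is planned, and the size of any effect of training on them cannot be derived from the documents. What remains is that baseline, in Section 7.3.1, is a loose label.

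**Conclusion.** The point holds as two mismatches in the printed instrument. One of three declared clinician characteristics has no question, and one of three post-MiADE correctness items names the wrong data type. The severity is minor, because the loss is confined to one exploratory correlate and one descriptive survey item, both in the outpatient study (25 clinicians at minimum, 50 at target, Section 10.4). For inpatient clinicians, the missing expertise item affects only the description in Section 7.3.1, since the correlations in Section 10.6.4 are for outpatients.

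This rests on two assumptions: that the questionnaires in Section 4 are the ones to be issued, and that no separate baseline form exists, as Appendix 1 indicates.

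**What to change.** Before the survey is issued:

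1. Add one item to the pre-MiADE questionnaire, for all clinicians, asking them to rate their own expertise with the EHR system. If the sponsor does not want it, delete the claim from Section 7.3.1 and align the Study 1 sentence in Section 4. Adding the item is preferable because it keeps the characteristic available for Section 10.6.4.
2. In the outpatient post-MiADE medication block, change the stem of the correctness item so that it refers to entering medications. The rest of the item can stay.
3. In Section 7.3.1, describe the survey as post-training and pre-switch-on instead of baseline. Its timing need not change.

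The cost is one added question, one corrected stem in an electronic survey and a small text edit. No participant contact is added and no analysis changes.
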